Gore et al, Clin Cancer Research [3]	I	27 patients with refractory solid tumors and lymphomas	Part 1: Entinostat 2, 4, or 6 mg/m ² PO every 2 weeks Part 2: Entinostat 2 mg/m ² twice weekly for 3 of 4 weeks Part 3: Entinostat 4 or 5 mg/m ² weekly for 3 of 4 weeks	MTD: 6 mg/m² every other week or 4 mg/m² weekly for 3 weeks followed by 1 week of rest DLT: Hypophosphatemia and asthenia were dose limiting on the weekly and twice-weekly dosing schedules no dose-limiting toxicity on every other week schedule

Batlevi et al, Haematologica [4]	II	49 patients with relapsed /refractory Hodgkin lymphoma	Part 1: Entinostat 10 to 15 mg PO every 2 weeks (Days 1 and 15) of a 4-week cycle Part 2: Entinostat 15 mg Days 1, 8, and 15 of a 4-week cycle	Most frequent grade 3 and 4 AE: thrombocytopenia (63%), anemia (47%), neutropenia (41%), leukopenia (10%), hypokalemia (8%), and hypophosphatemia (6%). Does reduction/delays: 51% of patients
Solid malignancies				
Denis et al, JCO 2014 (abstract) [5]	I/	ER+ breast cancer or NSCLC	Cycle 1: All patients: Entinostat 10 mg PO on Day 1 under fed conditions and on Day 15 under fasted conditions or on Day 1 under fasted conditions and on Day 15 under fed conditions. Cycle2: Breast cancer: Entinostat 10 mg PO on Days 1 and 15 at least 2 hours after breakfast followed by a \geq 1-hour fast every 28 days + exemestane 25 mg QD PO NSCLC: Entinostat 10 mg PO on Days 1 and 15 at least 2 hours after breakfast followed by a \geq 1-hour fast every 28 days + erlotinib 150 mg QD PO	Entinostat was well tolerated with no unexpected toxicities Results only published in abstract form without many details provided
Hausschild et al, Melanoma Research [6]	II	28 patients with non-resectable metastatic melanoma	Arm A: Entinostat 3 mg Days 1 and 15 of 4-week cycle Arm B: 7 mg Days 1, 8, 15 of 4-week cycle	No treatment-related serious adverse events occurred. Toxicity was mild to moderate with nausea (39%) and hypophosphatemia (29%) as the most frequently reported events. occurrence of the most common adverse events was similar in both treatment arms

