 - Grade 2-4 hypophysitis or pan-hypopituitarism requires holding pembrolizumab (MK-3475) and discontinuing treatment if unable to reduce corticosteroid dose to ≤ 10 mg of prednisone or equivalent per day within 12 weeks.
 - Grade 4 amylase or lipase abnormalities that are not associated with diabetes mellitus, associated liver or gall bladder inflammation clinical manifestations of pancreatitis and which decrease to <Grade 4 within 1 week of onset may stay on study.
 - Any drug-related liver function test (LFT) abnormality that meets the following criteria requires discontinuation: Grade 3 AST or ALT ($>5 \times$ ULN) and total bilirubin $>3 \times$ ULN.
 - Grade 3 drug-related thrombocytopenia >7 days or associated with bleeding

requires discontinuation.

- Any patient requiring systemic steroid or other immunosuppressive treatment.
- For patients with skin-only toxicity, when symptoms improve to \leq Grade 1, steroid taper should be started and continued over no less than 4 weeks. Discontinue MK-3475 if unable to reduce corticosteroid dose for irAEs to \leq 10 mg. pembrolizumab (MK-3475) treatment may be restarted and the dose modified as specified in the protocol.
- Patients with peripheral thyroiditis and no other autoimmune/inflammatory event may be restarted after a short course of steroids on a stable replacement regimen.
- Any dosing interruption lasting $>$ 12 weeks with the following exceptions:
 - Dosing interruptions $>$ 12 weeks that occur for non-drug-related reasons may be allowed if approved by the Principal Investigator. Prior to re-initiating treatment in a subject with a dosing interruption lasting $>$ 12 weeks, the Principal Investigator must be consulted.
 - Tumor assessments should continue as per protocol even if dosing is interrupted.

The reason(s) for protocol therapy discontinuation, the reason(s) for study removal, and the corresponding dates must be documented in the Case Report Form (CRF).

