5.8 Criteria to Resume Treatment

For non-autoimmune or inflammatory events, patients may resume treatment with study drug when the drug-related AE(s) resolve to Grade ≤ 1 or baseline value, with the following exceptions:

- Patients may resume treatment in the presence of Grade 2 fatigue.
- Patients with baseline Grade 1 AST/ALT or total bilirubin who require dose delays for reasons other than a 2-grade shift in AST/ALT or total bilirubin may resume treatment in the presence of Grade 2 AST/ALT OR total bilirubin.
- Patients with combined Grade 2 AST/ALT AND total bilirubin values meeting study parameters outlined in Section 5.4 should have treatment permanently discontinued.
- Non-drug-related toxicity including hepatic, pulmonary toxicity, diarrhea, or colitis, must have resolved to baseline before treatment is resumed.
- Drug-related endocrinopathies (not including drug-related adrenal insufficiency or hypophysitis) adequately controlled with only physiologic hormone replacement may resume treatment after replacement correction and clinically stable regimen.

If the criteria to resume treatment are met, the patient should restart treatment no sooner than the next scheduled time point per protocol. However, if the treatment is delayed past the next scheduled time point per protocol, the treatment should resume at the earliest convenient point that is within the 12 week delay period.

If treatment is delayed >12 weeks, the patient must be permanently discontinued from study therapy, except as specified in [Section 5.4](#) (Duration of Therapy).

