6.1.1 Dose Modifications: see tables below

6.1.2 Dose Modifications: see tables below

6.1.3 Table of Dose Modifications and Supportive Care Guidelines

Dose Level	Entinostat Dose
-1	8 mg, po D1
+1	8 mg, po D1, D8
+2	8 mg, po D1, D8, D15

Note: All treatment modifications must be expressed as a specific dose or amount rather than as a percentage of the starting or previous dose.

Nausea	Management/Next Dose for Entinostat
≤ Grade 1	No change in dose
Grade 2	Hold until ≤ Grade 1. Resume at same dose level.
Grade 3	Hold* until < Grade 2. Resume at one dose level lower, if indicated.**
Grade 4	Off protocol therapy

*Patients requiring a delay of >2 weeks should go off protocol therapy.

Nausea	Management/Next Dose for Entinostat
**Patients requiring > two dose reductions should go off protocol therapy.	
Recommended management: antiemetics.	

Vomiting	Management/Next Dose for entinostat
≤ Grade 1	No change in dose
Grade 2	Hold until ≤ Grade 1. Resume at same dose level.
Grade 3	Hold* until < Grade 2. Resume at one dose level lower, if indicated. **
Grade 4	Off protocol therapy
*Patients requiring a delay of >2 weeks should go off protocol therapy.	
**Patients requiring > two dose reductions should go off protocol therapy.	
Recommended management: antiemetics.	

Diarrhea	Management/Next Dose for entinostat
≤ Grade 1	No change in dose
Grade 2	Hold until ≤ Grade 1. Resume at same dose level.
Grade 3	Hold* until < Grade 2. Resume at one dose level lower, if indicated. **
Grade 4	Off protocol therapy
*Patients requiring a delay of >2 weeks should go off protocol therapy.	
**Patients requiring > two dose reductions should go off protocol therapy.	
Recommended management: Loperamide antidiarrheal therapy Dosage schedule: 4 mg at first onset, followed by 2 mg with each loose motion until diarrhea-free for 12 hours (maximum dosage: 16 mg/24 hours) Adjunct anti-diarrheal therapy is permitted and should be recorded when used.	

For other non-hematological toxicities that are grade 2 and do not resolve within a week, the investigator can reduce the entinostat dosing by one dose level (e.g. go from DL2 dosing to DL1 dosing).

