Given the frequent occurrence of severe cytopenias among patients with MDS and AML which are disease and not drug related and that worsening of cytopenias is a common occurrence during the disease course, the below dose modifications of entinostat for hematologic adverse events are considered guidance for the treating investigator and not mandatory. The decision to modify/hold dose will be at the discretion of the treating investigator and should include consideration of the clinical situation including severity consideration of baseline counts.

Hematologic adverse events	Dose Modifications

\geqGrade 3 neutropenia, \geqGrade 3 thrombocytopenia,
	
Administer symptomatic remedies/ start prophylaxis. Hold dose¹ until recovery to Grade 1 or study baseline under the following direction:
 
 1. If not recovered by next scheduled dose, skip the dose. If recovered by next scheduled dose, resume study drug at prior dose. 2. If receiving 8 mg dose on day 1 and 8, and not recovered by either of the next 2 scheduled doses, permanently discontinue study treatment. Otherwise, skip each dose. If recovered for either of these doses, resume study drug as follows: 
 • If receiving 8 mg on days 1 and 8, restart study drug at 8 mg only on day 1. • If receiving 8 mg on days 1, 8, and 21, restart study drug at 8 mg only on days 1 and 8. 3. If not recovered within 4 weeks, permanently discontinue study drug.

Recurrence of the same hematologic toxicity
	
 1. If the same hematologic toxicity recurs: 
 • Administer symptomatic remedies/ start prophylaxis. Hold¹ dose until recovery to Grade 1 or baseline. 2. If recovered within 2 weeks, resume study drug as follows: 
 • If receiving 8 mg on days 1 and 8, restart study drug at 8 mg on day 1 only • If receiving 8 mg on day 1 only, permanently discontinue study drug 3. If the same \geq Grade 3 event recurs (i.e., third occurrence) despite entinostat dose reduction to 8 mg on day 1 only, as described above, permanently discontinue study drug.

* Therapy emergent neutropenia or thrombocytopenia is defined as 50% or more reduction from the baseline.

1 If greater than 50% of doses are missed during any 6-week period, discontinue from study drug treatment.

There will be no dose modification for anemia

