	3	Yes	Toxicity resolves to Grade 0-1 or baseline	May increase the dosing interval by 1 week for each occurrence	Toxicity does not resolve within 12 weeks of last infusion
	4	Yes	N/A	N/A	Subject must be discontinued

In case toxicity does not resolve to Grade 0-1 within 12 weeks after last infusion, trial treatment should be discontinued. With Principal Investigator agreement, subjects with a laboratory adverse event still at Grade 2 after 12 weeks may continue treatment in the trial only if asymptomatic and controlled. Patients who experience a recurrence of the same severe or life-threatening event at the same grade or greater with re-challenge of pembrolizumab (MK-3475) should be discontinued from trial treatment.

AE-specific pembrolizumab (MK-3475) Dose Modifications and Supportive Care Guidelines:

The table below includes recommendations on the management of specific AEs and when to hold and/or discontinue pembrolizumab (MK-3475). These guidelines are intended to be applied when the investigator determines the events to be treatment-related. Note: if after the evaluation the event is determined not to be related, the investigator does not need to follow the treatment guidance. Therefore, these recommendations should be seen as guidelines and the treating physician should exercise individual clinical judgment based on the patient.

Given the frequent occurrence of severe cytopenias among patients with MDS and AML which are disease and not drug related and that worsening of cytopenias is a common occurrence during the disease course, the below dose modifications of pembrolizumab (MK-3475) for hematologic adverse events are considered guidance for the treating investigator and not mandatory. The decision to modify/hold dose will be at the discretion of the treating investigator and should include consideration of the clinical situation including severity consideration of baseline counts.

AE-Specific Dose Modification Guidelines for Drug-Related Adverse Events

Event(s)	CTCAE v4.0 Grade	Management / Next Dose for pembrolizumab (MK-3475)	Action / Supportive Care Guidelines

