Skin events • Pruritus • Rash • Rash generalized • Rash maculo-papular • Dermatitis exfoliative • Erythema multiforme • Steven's Johnson syndrome • Toxic epidermal necrolysis See 6.1.3 for immediate evaluation for skin events	Grade 2	No change in dose	
 Symptomatic treatment should be given such as topical glucocorticosteroids (e.g., betamethasone 0.1% cream or hydrocortisone 1%) or urea-containing creams in combination with oral anti-pruritics (e.g., diphenhydramine HCl or hydroxyzine HCl). Treatment with oral steroids is at investigator discretion for Grade 2 events.
	Grade 3	Hold pembrolizumab (MK-3475).	
 Consider Dermatology consultation and biopsy for confirmation of diagnosis. Treatment with oral steroids is recommended, starting with 1 mg/kg prednisone or equivalent once per day or dexamethasone 4 mg four times orally daily. When symptoms improve to \leqGrade 1, steroid taper should be started and continued over no less than 4 weeks. Permanently discontinue for inability to reduce corticosteroid dose to \leq10 mg of prednisone or equivalent per day within 12 weeks.
	Grade 4	Permanently discontinue pembrolizumab (MK-3475).	
 Dermatology consultation and consideration of biopsy and clinical dermatology photograph. Initiate steroids at 1-2 mg/kg prednisone or equivalent. When symptoms improve to \leqGrade 1, steroid taper should be started and continued over no less than 4 weeks.
Thrombocytopenia	\leq Grade 1	No change in dose	
	Grade 2	No change in dose	
	Grade 3	No change in dose	
 Grade 3 drug-related thrombocytopenia $>$7 days or associated with bleeding requires discontinuation.
	Grade 4	Hold pembrolizumab (MK-3475) until resolves to \leq Grade 1. May increase the dosing interval by 1 week.	
 Grade 4 drug-related thrombocytopenia $>$7 days or associated with bleeding requires discontinuation.
Vomiting	\leq Grade 1	No change in dose	
 Vomiting should be treated aggressively, and consideration should be given in subsequent cycles to the administration of prophylactic antiemetic therapy according to standard institutional practice. Patients should be strongly encouraged to maintain liberal oral fluid intake.

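### Sections 5.5 and 6 give different stopping rules for the same non-immune toxicity, often without naming the drug, and no text says which section governs

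*Combined protocol and SAP*

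**What the plan says.** **Thrombocytopenia**

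- Section 5.5 places "Grade 3 drug-related thrombocytopenia >7 days or associated with bleeding" among the events requiring discontinuation and names no drug. The item stands in a sub-list of exceptions to an allowance for laboratory abnormalities, and the lead-in to that sub-list refers to Principal Investigator approval. Section 5.7 removes from study those who meet the 5.5 criteria.
- The entinostat hematologic table in 6.1.3 holds the dose at grade 3 or above until recovery to grade 1 or baseline, after which it may resume. Its outer limit is: "If not recovered within 4 weeks, permanently discontinue study drug". On the two-dose schedule it also stops patients who have not recovered by either of the next two scheduled doses. The introduction says that these modifications "are considered guidance for the treating investigator and not mandatory".
- The AE-specific pembrolizumab table in 6.2.3 leaves the dose unchanged at grade 3, and adds in the same row that an event over 7 days "or associated with bleeding requires discontinuation". Its introduction says that modifications "for hematologic adverse events are considered guidance for the treating investigator and not mandatory".

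**Delays**

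- For grade 3 nausea, vomiting or diarrhea, the entinostat tables in 6.1.3 say: "Patients requiring a delay of >2 weeks should go off protocol therapy".
- For grade 3 nausea or vomiting, 6.2.3 lets pembrolizumab be held and discontinues it if there is no resolution within 12 weeks.
- Section 5.8 says: "If treatment is delayed >12 weeks, the patient must be permanently discontinued from study therapy", with an exception by cross-reference. Section 5.5 also uses 12 weeks for dosing interruptions.

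**Partial tie-breaks**

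- The opening of section 6 takes the more cautious option for delays and reductions of both drugs when causality is uncertain.
- The synopsis lets a patient continue on the drug not responsible when causality is clear.

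**The concern.** A site that sees a drug-related platelet fall finds a stop in one section and a discretionary hold in another, with nothing to rank them. A site that delays treatment for grade 3 nausea cannot tell whether the 2-week limit ends entinostat alone or both drugs.

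The stake is the dose-escalation cohort. Under section 5.2, cytopenia counts as a DLT only with prolonged treatment-associated aplasia, and a patient who does not complete two combined cycles is replaced. The choice of section can therefore decide whether a patient counts towards the MTD, which is the primary endpoint. Treatment duration would also vary by site for the same event.

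**Working it through.** The plan states no figure on this point, so the check sets the texts side by side.

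**1. One platelet event under each section.** Take drug-related grade 3 thrombocytopenia without bleeding, starting on day 2 of a combined cycle and back to baseline after 10 days (2 + 10 = day 12).

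- Section 5.5: 10 > 7 days, so discontinuation is listed as required, drug unspecified.
- Section 6.1.3: 10 < 28 days, and the day 8 dose is skipped. On the two-dose schedule (DL1) the next two scheduled doses are day 8 and day 22 (day 1 of the next cycle). The patient has recovered by the second, so entinostat restarts on day 1 only. On the three-dose schedule (DL2) the patient has recovered before day 15, but the restart row that would apply is written for days 1, 8 and 21. One skipped dose in 6 weeks, out of 4 (DL1) or 6 (DL2), is below the table's 50% missed-dose limit.
- Section 6.2.3: the 7-day stop applies to pembrolizumab, but as guidance.

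**2. Width of the disagreement.** The two limits are 7 days (7/21 = 0.33 cycle) and 28 days (28/21 = 1.33 cycles). On the two-dose schedule the window can close earlier, at the second scheduled dose without recovery.

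**3. Effect on the DLT count.** Suppose that this patient is one of three at a dose level and the other two are DLT-free.

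- Managed under 6.1.3, the patient can complete two combined cycles and count as DLT-free: 0 of 3, so escalate.
- Stopped under 5.5 before then, the patient is replaced. The count is 0 of 2 plus a newcomer. It becomes 0 of 3 if the newcomer has no DLT, or 1 of 3 and expansion to 6 if the newcomer has one.

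The same event can thus lead to a different next step.

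**4. Delay limits.** Two weeks is 14 days (0.67 cycle) and 12 weeks is 84 days (4 cycles), a six-fold difference. A 21-day hold for grade 3 nausea exceeds 14 and is below 84. If the 2-week rule stops entinostat only, the tables are compatible. If it stops both drugs, they conflict. The text supports either reading. Grade 3 nausea or vomiting is generally itself a DLT under 5.2, so this conflict bears mainly on treatment duration.

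**5. Do the tie-breaks settle it?** The section 6 rule covers delays and reductions under uncertain causality, not discontinuation. The synopsis rule covers clear causality, is not repeated in the parallel text of 5.1 or 13.1, and does not fit easily with removal under 5.7. Neither ranks 5.5 against section 6. The exception in 5.8 points to section 5.4 as Duration of Therapy, which is 5.5.

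**6. Gaps in the entinostat hematologic table.** No dose level uses days 1, 8 and 21. The recurrence row has instructions for the two-dose and one-dose schedules only. A patient on three doses who recovered by the next scheduled dose resumes at the prior dose, so can still be on that schedule when the toxicity recurs.

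**The case against.** The case on the other side narrows the point considerably, and much of it stands.

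- A reader might infer a three-way conflict, because the general pembrolizumab table does not hold treatment for hematologic grades 1 to 3. That table excludes toxicities listed in the AE-specific table, and thrombocytopenia is listed there. The AE-specific row reads as a sequence: no change, then stop after 7 days or with bleeding. It agrees with 5.5; only its non-mandatory status differs.
- A reader might infer that limits of 2, 4 and 12 weeks contradict each other by being different. They are largely specific to a drug and a toxicity, and 12 weeks can serve as an outer cap. What remains is that some limits do not name the drug that stops.
- Section 5.5 is not plainly unconditional, given its lead-in. That leaves its status unclear; it does not make it subordinate to section 6.
- It could be said that 5.5 covers drug-related cytopenia and the discretion in section 6 covers disease-related cytopenia. This fails: section 6.1 and the AE-specific table in 6.2.3 are both headed for drug-related events.
- The safety committee, Principal Investigator sign-off and at least monthly calls may bring practice into line. They do not tell a site which rule applies when the event occurs.

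**Conclusion.** The inconsistency is real but confined to three things: the 7-day thrombocytopenia stop in 5.5 against the discretionary entinostat hold of up to 4 weeks in 6.1.3, with the pembrolizumab version made non-mandatory in 6.2.3; delay limits that do not say whether one drug or both stop; and two faulty rows in the entinostat table. It should be corrected, because one patient counted or replaced is a sixth to a third of a dose-level cohort.

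The effect on the DLT count assumes that the event is judged drug-related, falls before two combined cycles are complete, and is handled under different sections at different sites.

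Two stronger conclusions are not supported. A reader might carry over the 63% rate of grade 3 and 4 thrombocytopenia from the Hodgkin lymphoma study in the section 5.1 table. That study used 10 to 15 mg per dose against 8 mg here and pooled both grades, and nothing gives the share that was drug-related or lasted over 7 days. No reliable frequency follows. A reader might also infer a distorted response denominator, but section 13.5.2 keeps early leavers in the main response analysis. The effect there is on exposure only.

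**What to change.** Amend the protocol so that sections 5.5, 5.8, 6.1.3 and 6.2.3 agree:

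1. State which section governs when they differ.
2. State whether the thrombocytopenia stop is mandatory or discretionary, including what Principal Investigator approval in the 5.5 lead-in applies to.
3. For each stop and delay limit, name the drug or drugs that it ends, consistently with the synopsis rule on continuing the other drug.
4. Reconcile the entinostat hematologic table with the dose-level table so that every dose level has an instruction, including on recurrence, and correct the cross-reference in 5.8.

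Which clinical limits apply is for the sponsor to decide.

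Until then, add to the stop reason on the CRF, which 5.5 and 5.7 already require, a code for the rule that triggered the stop. DLT denominators and replacements can then be audited. The cost is amendment wording and one CRF code, with no added visits or patients.

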5.6 Duration of Follow Up

Patients will be followed closely throughout the study period and for 6 months after the last dose of entinostat in combination with pembrolizumab (MK-3475) or 6 months after they are removed for the presence of any toxicity (early or late).

During maintenance: Patients whose primary oncologist is at one of the study sites will be followed and seen by a member of the study team at least monthly in person or by phone when study visits are not required. For patients who are followed by an oncologist outside of one of the study sites, a study team member will evaluate the patients at least monthly in person or by phone.

During 6 months post last dose or after removal from study: all patients will be evaluated by the study team at least monthly. Evaluations may be done during routine clinic visits in patients followed longitudinally at the study Cancer Center or via phone if in person visits are not possible due to logistical reasons. The study team will note the follow-up in the medical records and source documents will be sought for any change in condition related to the study or study drug.

Patients removed from study for unacceptable adverse event(s) will be followed in person or by phone until resolution or stabilization of the adverse event OR for at least 6 months after removal from study. Prior data have showed a median OS of 5 months for patients with HR-MDS who

failed 5-AZA or Decitabine. Therefore, we expect to capture most events of progression, relapse or death during the maintenance and follow-up phases of the study. For patients who are still alive at end of follow-up period, we will check social security Death Index every 3 months for 2 more years to obtain death dates for OS calculations

